10.3 Aim-specific analyses

Tests of statistical significance will not be undertaken for baseline characteristics; rather, the clinical importance of any imbalance will be noted.

10.3.1 Treatment Success and Safety

A superiority framework will be used for these analyses, with statistical significance defined as p<0.05 for each of the two primary outcomes. No multiplicity correction will be employed.

For each of the primary outcomes, if fewer than 5% of failures (unsuccessful treatment; specified Grade 2 event) occur in households with 2 or more failures, p-values will be calculated using Fisher's exact test, and 95% confidence intervals (CI) for risk differences will be calculated using the standard asymptotic formula.

Otherwise, within-household correlation will be accounted for using generalized estimating equations with logit link (for p-value) or identity link (for risk difference CI) and exchangeable correlation structure. If there are convergence problems with the risk difference estimation, a log link function will be used, with delta-method-constructed confidence intervals for risk differences.

Subgroup analyses will be performed by:

Site Sex Age (dichotomized at overall median) Weight (dichotomized at overall median)

Interaction tests will assess differential effects.

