15.8.3 Analysis Plan

Analyses will be intention-to-treat for both primary outcomes of successful completion and safety. For the successful completion outcome, losses to follow up (at 4 weeks for Arm 1HP and 12 weeks for Arm 3HP) will be considered as unsuccessful; a sensitivity analysis will be conducted among those not lost in both arms as of 12 weeks. For the safety outcome as of 24 weeks, losses will be considered as failures (safety events).

For the primary outcomes, if fewer than 5% of failures occur in households with 2 or more failures, p-values will be calculated using Fisher's exact test, and 95% confidence intervals (CI) for risk differences will be calculated using the standard asymptotic formula.

Otherwise, within-household correlation will be accounted for using

generalized estimating equations with logit link (for p-value) or identity link (for risk difference CI) and exchangeable correlation structure. If there are convergence problems, a log link function will be used, with delta-method-constructed confidence intervals.

Incidence of active tuberculosis will only be assessed during six months following enrollment but will be evaluated as an exploratory outcome. Incidence will be compared using Kaplan-Meier estimates at 24 weeks and Greenwood's variance formula. This will be a sufficiently rare event that within-household correlation will be ignorable. Censoring will be at last study visit or death. As a sensitivity analysis, TB-free survival will also be analyzed.

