In the BRIEF TB trial the rate of targeted safety events was 3%. We would want to demonstrate a reduction from 13% to at least as low as 6% in HIV-negative patients. With a CV of 0.1 (again, in reference to the maximum entropy distribution for the corresponding proportions, which are lower here than for the previous outcome), and the sample size of 250 individuals (about 125 households) in each study arm, we will have about 80% power for detecting a significant difference at a two-sided 0.05 significance level. We would also have 80% power to distinguish between risks of 12% and 5% in the two study arms. Although for convenience we have phrased this in terms of an hypothesis test, our goal is to estimate the difference in safety risks. With this sample size, and risks of 13% and 6% with 3HP and 1HP, respectively, the 95% CI for the risk difference will have a half-width of 3 percentage points. Reporting this CI will enable readers to make their own conclusions regarding non-inferiority of 1HP with respect to 3HP, in addition to superiority. (Dunn 2018)

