10.2 Outcome Definitions

10.2.1 Treatment completion and successful treatment

1HP

Completion of therapy is defined as having completed 28 daily doses of treatment within 6 weeks. Treatment success is defined as having taken at least 25 doses of medication confirmed by patient report and pill count, and having rifapentine or isoniazid detected at least once in urine or DBS specimens.

3HP

Completion of therapy is defined as having completed at least 12 weekly doses of treatment within 18 weeks. Treatment success is defined as having taken at least 11 doses of medication confirmed by patient report and pill count, and having rifapentine or isoniazid detected at least once in urine or DBS specimens.

Figure 2 shows the algorithm that will be used to classify patients as having treatment success of failure. This hierarchical approach begins with self-reported adherence, then uses pill count, and finally a composite of test results for isoniazid in urine and rifapentine and des-RPT in DBS.

[figure not shown]

Figure 2 Treatment Success

For the treatment success outcome, note that when loss to follow up precludes being able to demonstrate the requisite number of doses having been taken, the outcome is classified as "unsuccessful." A sensitivity analysis will be conducted among those who complete their last scheduled visit after 23 weeks on study.

10.2.2 Safety: Numbers of participants with at least one occurrence of Grade 2 or higher targeted safety events and/or discontinuation of study medications because of side effects attributed to study medications.

Targeted safety events are hypersensitivity syndrome, rash, peripheral neuropathy, hepatotoxicity, nausea and vomiting, and drug-related fever.

This study will grade toxicity and adverse events according to the *Division of AIDS (DAIDS) Table for Grading Adult and Pediatric Adverse Events, Corrected Version 2.1* (dated July 2017).

https://rsc.niaid.nih.gov/sites/default/files/daidsgradingcorrectedv21.pdf See Appendix V of the study protocol.

For the primary safety outcome as of 24 weeks, those who do not complete their last scheduled visit after 23 weeks on study will be considered as failures (safety events).

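### The primary test is chosen from the outcome data by a share that does not isolate household correlation, site is left out, and the safety failure is worded too narrowly: a small cost and a free fix

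*SAP*

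**What the plan says.** Households, of at most two participants, are randomised as a unit, stratified by site (SAP 5, protocol 15.5). For both primary outcomes protocol 15.8.3 states that "if fewer than 5% of failures occur in households with 2 or more failures, p-values will be calculated using Fisher's exact test", with an ordinary asymptotic interval for the risk difference. SAP 10.3.1 repeats the rule: where fewer than 5% of failures "occur in households with 2 or more failures, p-values will be calculated using Fisher's exact test". Otherwise GEE with exchangeable correlation is used, with "logit link (for p-value) or identity link (for risk difference CI"). Site appears in SAP 10.3.1 only in the list of subgroup analyses.

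Inside the rule, SAP 10.3.1 describes the events as "failures (unsuccessful treatment; specified Grade 2 event"). SAP 10.2.2 defines the safety outcome more widely. It counts "Grade 2 or higher targeted safety events and/or discontinuation of study medications because of side effects attributed to study medications", and adds that "those who do not complete their last scheduled visit after 23 weeks on study will be considered as failures (safety events"). Protocol 15.8.3 agrees on losses: "For the safety outcome as of 24 weeks, losses will be considered as failures (safety events").

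SAP 6 describes household variation by a coefficient of variation (CV): 0.15 for treatment success and, for safety, "With a CV of 0.1 (again, in reference to the maximum entropy distribution for the corresponding proportions, which are lower here").

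**The concern.** Randomisation by household already justifies a clustered analysis, so no trigger is needed. The trigger used is also a poor gauge of clustering. The share of failures in double-failure households rises with within-household correlation, but also with the failure rate and with the proportion of households that contribute two people.

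Three things follow. The method behind each primary p-value is unknown until outcomes are in. In either branch the p-value and the interval come from different calculations and can point different ways. That matters for safety, because SAP 6 says the aim is to estimate the difference and let readers judge from the interval. Finally, leaving out the stratification factor makes the standard error too large if the sites differ in outcome.

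The wording gap is a separate matter. If the trigger counts adverse events only while the outcome also counts losses, the trigger cannot respond to losses that cluster within households.

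**Working it through.** **Inputs.** From SAP 6 and protocol 15.4: success 80% (3HP) and 90% (1HP), so failure 20% and 10%; safety events 13% and 6%; 250 people in about 125 households per arm; CV 0.15 and 0.1; two-sided 0.05. Not in the documents, so assumed: loss rates, loss clustering, site differences, and an average household size of 1.8.

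**1. The plan's own figure.** Households per arm = 1 + (1.96 + 0.84)² × [p0(1−p0)/2 + p1(1−p1)/2 + CV²(p0² + p1²)] / (p0−p1)². For success the bracket is 0.08 + 0.045 + 0.0225 × (0.64 + 0.81) = 0.1576. The result is 124.7 households, so 125 households (250 people) give power of 80.1%. The stated 80% reproduces.

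**2. Implied household correlation.** ICC = CV² × p/(1−p).
- Success: 0.0225 × 0.8/0.2 = 0.09 (3HP) and 0.0225 × 0.9/0.1 = 0.2025 (1HP).
- Safety: 0.01 × 0.13/0.87 = 0.0015 (3HP) and 0.01 × 0.06/0.94 = 0.0006 (1HP).

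**3. Expected share of failures in double-failure households, all pairs.** Share = Σ[p² + ICC × p(1−p)] / Σp over the two arms.
- Treatment failure, ICC 0: (0.04 + 0.01)/0.30 = 16.7%. With the plan's ICCs: (0.0544 + 0.0282)/0.30 = 27.5%.
- Safety, ICC 0: (0.0169 + 0.0036)/0.19 = 10.8%. With ICC 0.1: 0.03745/0.19 = 19.7%.
- Safety with independent loss L counted as failure, p′ = p + L(1−p), ICC 0: 13.2%, 14.8% and 19.1% at L = 3%, 5% and 10%.

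Without any correlation, the expected share falls to 5% only at an average household size of about 1.18 (treatment failure) or 1.30 (safety).

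**4. What the rule costs.** Simulation used 100,000 trials per cell, 125 pairs per arm and two sites of 63 and 62 households per arm. Monte Carlo SE is at most 0.16 points on power and 0.08 on null rejection. The rule was run as written, with the full safety definition. The fix is an arm-and-site logistic GEE with household-robust SE, tested on the standardised risk difference, with variance multiplied by K/(K−3) and t on K−3 degrees of freedom (K households). Safety, 13% against 6%, plan ICCs:

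| Loss | Fisher chosen (no site gap) | Power, rule v fix, no site gap | Power, rule v fix, 10-point site gap | p-value and CI disagree under the rule (no site gap) |
|---|---|---|---|---|
| 0% | 22% | 75.0% v 77.1% | 75.0% v 78.2% | 2.1% |
| 3% | 8.5% | 63.4% v 64.6% | 62.9% v 65.4% | 1.7% |
| 5% | 3.3% | 56.9% v 57.4% | 56.1% v 58.0% | 1.2% |
| 10% | 0.4% | 44.0% v 44.1% | 43.2% v 44.3% | 0.8% |

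The fall down the power columns comes from counting losses as events, not from the test. With the fix the p-value and interval never disagree.

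Other settings:
- Average household 1.8 (111 pairs and 28 singles per arm): 74.8% v 77.0% with no loss; 56.8% v 57.5% at 5% loss.
- Safety ICC 0.1, no loss: Fisher chosen in 3%; 72.1% v 73.0%.
- Success, plan ICCs: Fisher essentially never chosen; 83.4% v 84.2%, 83.6% v 84.5% and 83.5% v 85.2% at site gaps of 0, 5 and 10 points.

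Null rejection was 4.0–5.0% (rule) v 5.0–5.2% (fix) for safety, and 4.4–5.0% v 4.8–5.1% for treatment failure. Without the small-sample correction, the fix has 0.4–0.9 points more power and null rejection of 5.0–5.4%.

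**5. Narrow trigger.** Suppose the trigger counts events only and the outcome counts losses. At the planned rates Fisher is then chosen in 22% of trials whether loss is 3%, 5% or 10%. Null rejection at 5% and 10% loss:
- losses independent: 4.5–4.6%;
- half the loss rate is whole-household loss: 5.0% and 5.3%;
- both members always lost together: 5.3% and 6.1%, against 5.0–5.1% in the same case with the full definition.

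**The case against.** The rule is prespecified, can be applied without knowing the arms, and errs safely. Because the share usually exceeds 5%, it leans towards GEE, which is valid with or without correlation. For success the 5% rule has no practical effect: Fisher is almost never chosen, and without a site gap the gain there comes from testing the risk difference. For safety with no loss, dropping the rule moves power from 75.0% to 76.6%; the remaining 0.5 points come from the other changes. Part of the gain simply reflects the rule's slightly conservative size. SAP 10.3.1 defines significance by the p-value, so an interval that disagrees does not change the formal verdict, and reporting a model or exact p-value beside a risk-difference interval is common.

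The site effect is assumed. A 10-point gap centred on 6% means about 1% against 11% within the 1HP arm. At a 5-point gap, safety power was 74.9% v 77.5%, against 75.1% v 77.3% with no gap (20,000 trials per cell), so site adds only about 0.4 points. The narrow safety wording may be shorthand, since SAP 10.2.2 also calls non-completers failures.

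All of this stands, and it sets the priority. It does not give a reason to keep the rule. The narrow phrase sits in the sentence that selects the test, so a programmer could implement either reading.

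**Conclusion.** The point holds as a low-priority improvement. The trigger mixes failure rate and household size with correlation, the stratum is missing from both branches, and the safety failure in SAP 10.3.1 does not match 10.2.2.

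The cost is efficiency and consistency, not validity. Without a site gap, safety loses 2.1 points of power with no losses and 0.1 to 1.2 points at losses of 10% to 3%; success loses 0.8 points. With an assumed 10-point site gap the cost is 1.1 to 3.2 points for safety and 1.7 for success. Type I error is not inflated under the full definition. It exceeds 5% appreciably only if the narrow trigger is combined with strongly clustered losses, up to 6.1% in the most extreme case examined. Event rates and ICCs are the plan's; loss rates, loss clustering and site gaps are assumptions.

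**What to change.** In SAP 10.3.1 and protocol 15.8.3, delete the 5% rule. For each primary outcome prespecify one household-clustered GEE (logit link, exchangeable correlation, robust SE) with arm and site. From that model report the standardised risk difference with its 95% interval, and take the p-value from the same risk difference and SE. If the model cannot be fitted, use a site-stratified risk difference with a household-robust SE; this fallback depends on model failure, not on how failures fall within households. A small-sample variance correction is optional, but state whether it will be used.

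Replace the safety wording in SAP 10.3.1 with a reference to the full 10.2.2 definition: targeted events of Grade 2 or higher, discontinuation for side effects, and non-completion of the final visit.

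The cost is wording in two sections and a few lines of code. Site and household are already recorded, so no participants or data are added.

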The total incidence of all adverse effects from isoniazid is approximately 5%, many of which do not require discontinuation of the drug. Peripheral neurotoxicity is dose dependent and it is uncommon (<0.2%) at conventional doses. The risk of peripheral neuritis increases for persons who are malnourished or predisposed to neuritis by other illnesses. Concomitant administration of pyridoxine (vitamin B₆) is recommended for these persons.

Other nervous system reactions are rare at normal doses, and they include convulsions, encephalopathy, optic neuritis, memory impairment, and psychosis. Gastrointestinal adverse effects include nausea, vomiting, and epigastric distress. Asymptomatic elevation of aminotransferases is common and occurs in 10-20% of persons receiving isoniazid. However, idiosyncratic severe hepatic reactions are uncommon but are more likely in older persons (up to 2.3% hepatitis incidence in persons more than 50 years old), and may be life threatening. Daily consumption of alcohol increases the risk of isoniazid-associated hepatotoxicity by approximately 4-fold.

WHO prequalified, ANVISA-approved isoniazid is available as 300 mg tablets and will be obtained from the Brazilian Ministry of Health.

Safety profile of study regimens

In June 1998, the US Food and Drug Administration (FDA) approved rifapentine (RPT) for the treatment of tuberculosis, the first new drug approved for tuberculosis in more than 25 years. In addition, the 3HP regimen is registered by the US FDA and is recommended for the prevention of TB disease by the US Centers for Disease Control and Prevention (CDC). The World Health Organization recommends 3HP for low burden, middle and high-income countries in the integrated guidelines for the programmatic management of LTBI. Tolerance of HP regimen was comparable to INH in the CPCRA/ACTG trial.

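### Both primary analyses use treatment arm alone, although age, sex, weight and screening ALT are available for everyone; the analysis is valid, but a possible modest gain in precision and pre-specified protection against chance imbalance go unused

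*SAP*

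**What the plan says.** SAP 10.3.1 gives two routes for each primary outcome. If fewer than 5% of failures fall in households with two or more failures, it uses Fisher's exact test and an asymptotic interval for the risk difference. Otherwise "within-household correlation will be accounted for using generalized estimating equations with logit link (for p-value) or identity link (for risk difference CI"), with an exchangeable correlation structure. Neither route names a baseline covariate or site, the randomisation stratum. Protocol 15.8.3 fixes the population ("Analyses will be intention-to-treat for both primary outcomes of successful completion and safety") and then gives the same two methods.

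Site, sex, age and weight appear in SAP 10.3.1 only as subgroup variables, with age and weight split at the median. SAP 10.3 says that the clinical importance of any baseline imbalance will be noted, and names no analysis to follow.

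The data exist. Protocol 12.1.1 takes weight and a chemistry panel with liver tests from everyone at screening, and Protocol 6.2.1 lists ALT in that panel. Age is an eligibility criterion, and age and sex must both be known for the planned subgroups.

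For safety, SAP 6 assumes "risks of 13% and 6% with 3HP and 1HP, respectively", "the sample size of 250 individuals (about 125 households) in each study arm" and "With a CV of 0.1", and states that "we will have about 80% power for detecting a significant difference at a two-sided 0.05 significance level". SAP 10.3.1 sets "statistical significance defined as p<0.05 for each of the two primary outcomes".

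**The concern.** A covariate measured before the first dose can sharpen a randomised comparison without changing its target, provided that the estimate remains a marginal risk difference. SAP 6 says that estimating the difference in safety risks is the goal. The documents give one reason to think that a listed variable is prognostic: Protocol 11.1.2 says that severe isoniazid liver reactions "are more likely in older persons (up to 2.3% hepatitis incidence in persons more than 50 years old"), and hepatotoxicity is a targeted safety event.

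There is also a pre-specification gap. SAP 1 aims to avoid data-driven analyses. If age or ALT is imbalanced by chance, however, the plan only has it noted, and any adjusted analysis would then be chosen after the imbalance had been seen. This matters more here because the trial is open-label. Allocation is also by household, so characteristics shared within a household balance over about 125 units per arm rather than 250.

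**Working it through.** **Inputs.** From SAP 6: safety risks 13% and 6%, 250 per arm in about 125 households, CV 0.1 for safety and 0.15 for treatment success, success rates 80% and 90%. SAP 6 and 10.3.1: two-sided 0.05. Assumed, because the documents give no value: R², the share of outcome variance explained by the covariates.

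**The plan's own figures.** The usual CV formula for cluster trials, with m = 2 per household, is

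c = 1 + (1.96 + 0.84)² × [p₁(1−p₁)/m + p₂(1−p₂)/m + CV²(p₁² + p₂²)] / (p₁ − p₂)²

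- Success, 80% vs 90%, CV 0.15: bracket = 0.08 + 0.045 + 0.0326 = 0.1576, so c = 124.7 households per arm. Reproduced: 80.1% power at 125.
- Safety, 12% vs 5%, CV 0.1: c = 123.9. Reproduced: about 80% power.
- Safety, 13% vs 6%, CV 0.1: bracket = 0.0566 + 0.0282 + 0.0002 = 0.0850, so c = 137.1. Not reproduced: 76.3% power at 125.

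Other methods for 13% vs 6% give 76.2% (pooled), 76.7% (unpooled), 77.5% (arcsine) and 72.7% (exact Fisher). The starting point is therefore about 76-77%, and the pooled calculation needs 275 per arm for 80%.

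**Effect of adjustment on safety.** SE = √[(0.13×0.87 + 0.06×0.94)/250] = √(0.1695/250) = 0.02604, so z = 0.07/0.02604 = 2.688. The half-width is 1.96 × 0.02604 = 5.1 points. (SAP 6 states 3 points, which is a separate correction.) Adjustment multiplies the variance by (1 − R²), so z becomes 2.688/√(1 − R²), and power = Φ(z − 1.96). The CV formula starts from z = √(124 × 0.0049/0.08496) = 2.674.

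| Assumed R² | z (unpooled) | Power, unpooled | Power, CV formula | Half-width (points) |
|---|---|---|---|---|
| 0 | 2.688 | 76.7% | 76.3% | 5.10 |
| 1% | 2.702 | 77.1% | 76.7% | 5.08 |
| 2% | 2.716 | 77.5% | 77.1% | 5.05 |
| 5% | 2.758 | 78.8% | 78.3% | 4.97 |
| 10% | 2.834 | 80.9% | 80.5% | 4.84 |

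Reaching 80% needs R² of 7.9% (unpooled) or 8.9% (CV formula).

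**What R² means here.** With a normally distributed baseline score, an odds ratio of 1.5 per SD gives R² of about 1.6%, 2.0 gives about 4.6%, and 2.5 gives about 7.9%. In a simulation of 1,200 trials with two-person households, no added household correlation and an odds ratio of 1.5 per SD, the logit GEE rejected in 77.7% of trials unadjusted and 77.8% adjusted.

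**Treatment success.** From z = √(124 × 0.01/0.1576) = 2.805, the same step gives 80.1% at R² = 0, 80.5% at 1%, 80.9% at 2% and 82.1% at 5%. No passage links any listed covariate to adherence.

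**Feasibility.** Expected safety events are 250 × (0.13 + 0.06) = 47.5. Six model terms (arm, site, age, sex, weight, ALT) leave about 8 events per term. Treatment success has 250 × (0.20 + 0.10) = 75 failures for five terms, or 15 per term.

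Even with independent outcomes and two-person households, the share of failures in two-failure households is (0.13² + 0.06²)/0.19 = 10.8% for safety and (0.20² + 0.10²)/0.30 = 16.7% for success. Both exceed 5%, so the GEE route is the likely one, and that route can carry covariates.

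**The case against.** The strongest reply is that nothing is wrong with the plan. An unadjusted comparison in a randomised trial is valid for the risk difference, its type I error is unaffected, and it contradicts nothing else in the documents. That stands.

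The second reply is that the gain is speculative, and this largely stands too. Take the one cited figure at its most favourable: half the participants over 50, 2.3% hepatitis among them and none below 50 (both splits assumed). Explained variance is 0.25 × 0.023² = 0.00013 against an average within-arm variance of 0.1695/2 = 0.085. That is R² of about 0.16%, worth less than 0.1 point of power. Hepatotoxicity is only one of six targeted events, and discontinuations and losses also count as safety failures under SAP 10.2.2. Screening ALT is range-restricted by the exclusion of values above 3 times the upper limit.

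A reader might infer that adjustment would bring safety back to the stated 80%. The documents do not support that. R² of 5% is worth about 500/0.95 − 500 = 26 participants, against a shortfall of 2 × (275 − 250) = 50, and nothing in the documents suggests an R² near 8-9%. Counting losses as safety events costs far more: at an assumed 3% loss in both arms, power is about 64%.

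The case for naming covariates in advance survives these replies. It needs no new data, leaves the estimand alone, and settles beforehand a question that SAP 10.3 leaves open. Adjustment guards only against imbalance in the variables that are modelled.

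**Conclusion.** The point holds as an inexpensive improvement and not as an error. Both primary analyses use arm alone while four participant-level baseline variables are available for everyone. The plausible gain in safety power is roughly 0 to 2 points, and at R² of 5% the interval half-width shrinks by about 0.1 point. These figures rest on an assumed R², on the variance scaling with 1 − R², and on no within-household correlation beyond the plan's CV. It would be too strong to say that the plan demonstrably wastes useful precision, because the documents give no prognostic strength beyond the remark on age and hepatitis. The better-supported benefit is that the adjusted analysis would be fixed before any imbalance is seen. The gap between about 76-77% and the stated 80% comes from the sample size for 13% vs 6% and should be handled as such.

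**What to change.** In SAP 10.3.1, and in matching words in Protocol 15.8.3:

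- Estimate each primary outcome's marginal risk difference from a logistic working model with arm, site, continuous age, sex and weight, adding screening ALT for safety.
- Standardise the predicted risks over all participants, and use a household-clustered variance for both the confidence interval and the p-value. Standardisation matters because covariates placed directly in the logit GEE would turn its odds ratio into a conditional one.
- Keep the present unadjusted analysis as supporting.
- State a fixed fallback rule now: for example, use the unadjusted result if the model does not converge or if total events are below a number named in the SAP.
- Do not cite adjustment as the answer to the safety power shortfall; correct that figure separately in SAP 6.

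The cost is a few lines of text and code. The downside is slightly more modelling with about 48 expected safety events, and little return if the covariates prove weakly prognostic.

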9.1 Study Groups

Arm A (n=250): Experimental arm Rifapentine and isoniazid once daily for 4 weeks, 28 doses

Arm B (n=250): Control arm Rifapentine and isoniazid once weekly for 12 weeks, 12 doses

9.2 **Dosing Structure**

Dosing of rifapentine and INH will be based on the dosages given to individuals >50

kg in the BRIEF TB trial for arm A and current CDC guidelines for arm B. Based on a meta-analysis of the pharmacokinetics of rifapentine in nine clinical trials of preventive therapy conducted by Hibma and colleagues (Hibma, 2020), weightbanded dosing will not be used. This analysis demonstrated that weight-banded dosing results in sub-optimal exposures for lower weight patients, as drug clearance is not proportional to body weight. An ongoing trial of rifapentine for the treatment of active TB is currently underway and is using flat dosing of rifapentine at 1200 mg/day (TBTC Study 31/ACTG A5349) and no signals of toxicity have been reported with this dosage in lower weight individuals. In 2020, the WHO revised its guidelines for treating latent TB and recommended flat dosing of rifapentine for adolescents and adults, regardless of weight. (WHO)

Arm A Rifapentine: Isoniazid:	600 mg once daily for 4 weeks (28 doses) 300 mg once daily for 4 weeks (28 doses)
Arm B Rifapentine: Isoniazid:	900 mg once weekly for 12 weeks (12 doses) 900 mg once weekly for 12 weeks (12 doses)

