6. SAMPLE SIZE CONSIDERATIONS

The sample size target is 500 evaluable adolescents and adults. Having each participant complete all of the scheduled drug sampling evaluations will provide approximately 1000 rifapentine and isoniazid pharmacological data points.

Assumptions, Outcome 1:

Successful treatment with 3HP = 80%

In clinical trials, reported completion rates of 3HP have ranged from 84-92% with directly observed therapy. In the CDC-sponsored iAdhere Trial, completion of self-administered 3HP was only 74-76%. In this study, which will use self-administered treatment, we estimate a completion rate of 80%. (Belknap 2017)

Successful treatment with 1HP = 90%

Completion of self-administered 1HP was 97% in the BRIEF TB Study, which was undertaken at research clinics in the ACTG and IMPAACT networks. We estimate that in a more real-world setting adherence will be slightly lower, but should still be at least 90%. We believe that demonstrating \geq 90% completion for 1HP, significantly greater than with 3HP, will provide compelling evidence for clinical practice and treatment guidelines to change.

Based on these assumptions, with an average cluster (household contacts of the index case) size of nearly 2, and an outcome coefficient of variation (CV) of 0.15, near the mean bound using the maximum entropy distribution (Chatfield 2020), a sample size of 250 individuals per arm, 500 total, would provide 80% power for detecting a significant difference at a two-sided 0.05 significance level. The sample size is not inflated for losses to follow up, as those who fail to complete the protocol will have reached a study endpoint.

Assumptions, Outcome 2:

Proportion of participants experiencing Grade 2 or higher targeted safety events with 3HP = 13%.

In TBTC Study 26 and the iAdhere Study, rates of drug-related adverse events with 3HP were 7-8%. In clinical cohort studies, rates of discontinuation for adverse events have been higher. An analysis of patients taking 3HP in

Taiwan found that treatment discontinuation due to adverse events occurred in 12%. (Chan, ERJ 2018) A study of health care workers in South Korea reported that 19% of those receiving 3HP had hypersensitivity reactions and 15% discontinued 3HP due to drug reactions. (Jo 2019) We conservatively assume the rate will be 13%.

Proportion of participants experiencing Grade 2 or higher targeted safety events with 1HP = 6%.

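### SAP 10.3.1 tests whether the 1HP–3HP difference varies with age and weight by median split; a continuous term would use more of the information if the effect modification is roughly linear

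*SAP*

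**What the plan says.** SAP 10.3.1 plans subgroup analyses of both primary outcomes by site, sex, age and weight. The last two are given as "Age (dichotomized at overall median) Weight (dichotomized at overall median"), followed by the single sentence "Interaction tests will assess differential effects".

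The SAP does not spell out that the interaction test uses the two-category variable. That is the natural reading, since no linear, spline or trend version is mentioned. Protocol 15.8.3 contains no subgroup analyses, so SAP 10.3.1 is the only place where effect modification by weight is addressed.

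The same section sets the main tests up "with statistical significance defined as p<0.05 for each of the two primary outcomes", without multiplicity correction. It gives no significance level or power for the interaction tests. The main p-value comes from Fisher's exact test or, when failures cluster enough within households, from a logit-link GEE with exchangeable correlation. No model is named for the interaction test in either case.

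Protocol 9.2 assigns one fixed dose per arm regardless of weight, and people under 40 kg are excluded (Protocol 10.1.2, SAP 7.1.2).

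**The concern.** Age and weight are recorded as continuous measurements. Cutting each at its median treats a participant of 41 kg like one just under the median, and treats two people a kilogram apart on either side of the median as different in kind. If the treatment difference changes steadily along the scale, that coding discards information which a continuous term would use.

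The stakes are limited but real. The SAP itself chose weight as a possible modifier, the two arms differ in dose and schedule, and this is the only planned look at whether their difference in safety or success varies with weight. An interaction test in a trial sized for main effects is weak to begin with. Coding that weakens it further makes a non-significant result still less informative.

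**Working it through.** **1. The plan's own sample size.** Inputs from SAP 6: "Successful treatment with 3HP = 80" per cent, "Successful treatment with 1HP = 90" per cent, an "average cluster (household contacts of the index case) size of nearly 2", CV 0.15, and a sample that "would provide 80% power for detecting a significant difference at a two-sided 0.05 significance level". The standard formula for comparing proportions between clusters is

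c = 1 + (z₁ + z₂)² × [p₀(1−p₀)/m + p₁(1−p₁)/m + k²(p₀² + p₁²)] / (p₀ − p₁)²

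With m = 2 and k = 0.15 the bracket is 0.080 + 0.045 + 0.0225 × (0.64 + 0.81) = 0.1576, so c = 1 + 7.849 × 0.1576 / 0.01 = 124.7. That is 125 households, or 250 people, per arm, which reproduces the plan. This figure is for the main effect; none is given for interactions.

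**2. Information kept by a median split.** With 1:1 randomisation, the information on a linear treatment-by-covariate interaction that survives dichotomising is, to first order, the squared correlation between the covariate X and its above-median indicator D.

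For standard normal X: Cov(X, D) = 1/√(2π) = 0.399 and Var(D) = 0.25, so r² = 0.399²/0.25 = 2/π = 0.637. Then 500 × 0.637 ≈ 318.

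The documents give no covariate distributions, so shapes were assumed:

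| Assumed shape | Information kept |
|---|---|
| Normal | 64% |
| Weight, normal, truncated at 40 kg (mean 60–75, SD 10–18) | 65% |
| Weight, lognormal, truncated at 40 kg (same means and SDs) | 61–63% |
| Age, right-skewed | 60% |
| Uniform | 75% |

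**3. What this does to power.** Logistic interaction tests were simulated at the SAP's planning rates (success 80% v 90%; safety events 13% v 6%), with n = 500, 1:1 allocation, a normal covariate, two-sided 0.05 and clustering ignored. The interaction sizes are assumptions. Ranges show the spread between repeated simulations.

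| Assumed interaction (log-odds) | Success: continuous v split | Safety: continuous v split |
|---|---|---|
| None (type I error) | about 5%, both | about 5%, both |
| 0.25 per SD | 16% v 11% | 13% v 9% |
| 0.45 per SD | 38–41% v 25–26% | 28–30% v 16–19% |
| 0.8 per SD | 86% v 65–67% | 70–72% v 46–47% |
| Step at the median, ±0.45 | 25% v 35% | 17% v 23% |

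For scale, the mean difference between the two halves of a normal covariate is 2 × √(2/π) = 1.596 SD. An interaction of 0.45 per SD therefore means a contrast between halves of 1.596 × 0.45 = 0.72, against a planned main effect on success of ln(0.9/0.1) − ln(0.8/0.2) = 2.197 − 1.386 = 0.81. So 0.45 per SD is already a large interaction.

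The 64% is a first-order figure. At assumed interactions of 0.5 to 1.0 per SD, with normal or lognormal covariates, the squared ratio of median z-statistics (split to continuous) was 0.59–0.66 for success and 0.50–0.58 for safety.

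**The case against.** The strongest reply is that this is a conventional secondary analysis with little at stake. The overall median is a pre-specified rule computed across both arms. It cannot be tuned to the results and it gives balanced subgroups. Individual weights are collected, so a continuous analysis could be added later. With power of roughly 10% to 40% at interactions of 0.25 to 0.45 per SD, either coding will usually miss an interaction, and the change would rarely alter a conclusion. All of that stands. It limits the importance of the point but gives no reason to prefer the weaker test in advance.

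The advantage also depends on shape. If the true effect is a step at the median, the split is the better test, as the last row of the power table shows. This too stands, and is why a linear term needs a check for non-linearity.

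A reader might go further and infer that the split weakens the trial's check on whether fixed dosing suits lighter participants. The documents do not support that. Both arms have fixed doses, so the interaction concerns only whether the 1HP–3HP difference varies with weight. Neither document links the weight subgroup to the dosing rationale. Protocol 9.2 says "This analysis demonstrated that weight-banded dosing results in sub-optimal exposures for lower weight patients"; that is its argument for fixed dosing, and does not flag a weight problem with it. The success outcome in SAP 10.2.1 is doses taken plus drug detected at least once, so any link to exposure bears mainly on safety.

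**Conclusion.** The point holds as a modest improvement to a secondary analysis. For roughly linear effect modification and a near-normal covariate, the planned split keeps about 64% of the information of a continuous term, and about 60% to 75% across the shapes tried. Under the assumed linear interactions of 0.25 to 0.8 per SD, that costs between 4 and 26 percentage points of power, with type I error about 5% for both codings.

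Three limits apply. The loss is conditional on linearity, so a flat statement that about a third of the information is thrown away would claim too much. The documents supply neither the covariate distributions nor an interaction size, so the power figures are illustrative. And the test addresses only the between-arm difference. The primary comparisons, the sample size and data collection are untouched.

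**What to change.** In SAP 10.3.1, state that:

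- the treatment-by-age and treatment-by-weight interaction tests use the baseline values as continuous, linear terms, with a pre-specified quadratic or spline check for non-linearity;
- these tests are run in the logit-link GEE with exchangeable household correlation, whichever of Fisher's exact test or GEE is used for the main comparison. Fisher's test cannot supply an interaction test, and an identity link with a continuous covariate risks fitted values outside 0 to 1;
- the median-split estimates are kept for display only.

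The cost is a few lines of SAP text. Weight is already recorded at screening (Protocol 12.1.1), so no new data, visits or participants are needed. The trade-off to acknowledge is reliance on approximate linearity, with less power than the split if the true effect is a step at the median.
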